Study protocol

Early mobilisation after surgery in patients with elbow fracture-dislocation

Handläggare: [name] PhD physiotherapist specialist
Verksamhet: Ortopedic clinic University hospital in Linköping
Datum: 2020 05 30

Study protocol elbow fracture-dislocations study

Background

Fractures in the elbow joint can affect young people in high-energy violence such as contact sports and falls from a great height. The type of fracture and the degree of fragmentation are determined by the direction and force of the violence. Older people can also suffer from elbow fractures after low-energy trauma. The elbow fractures can be combined with simultaneous dislocation of the radius or ulna in relation to the humerus and ligament injuries laterally or medially. Elbow dislocations represent 10% of all elbow injuries (Casanova et al). The degree of dislocation and joint surface involvement determines whether surgery is appropriate. In an elbow dislocation with simultaneous fracture of the ulna and or radius, surgery with internal fixation and or caput radi prosthesis is often indicated. After the surgery, the patients receive a plaster for a number of weeks, which can vary slightly depending on where in the country you are having surgery. Immobilization for 3 weeks is the most common post-operative recommendation (Ndeye Fatou Coulibaly et al). However, there is no scientific evidence to support that period of immobilization and patients are often very stiff when the plaster is removed and have difficulty getting started with range of motion exercises. A common complication of elbow fractures combined with soft tissue injuries is "stiff elbow" (Morrey et al). Stiffness in the elbow can be secondary to so-called "heterotopic ossification", which means that bone material is formed in normally soft tissues (Ring et al). This condition may be due to various factors and, among other things, the immobilization time after surgery seems to play a significant role (Abrams et al, Wiggers et al). Patients often become very stiff and in some cases when functional mobility cannot be achieved, patients need to undergo another operation (capsule release) in order to increase mobility in the elbow joint. After a capsule release, a tough rehabilitation period will follow. There is a prospective study (Giannicola et al) where 76 patients who had surgery after fracture dislocation in the elbow were followed. They reported that early range of motion exercises, initiated already 2 days postoperatively, had had good results. However, there are no randomized studies in the field. In light of this, we want to investigate whether a shorter immobilization time in a plaster and faster initiation with unloaded range of motion exercises could improve elbow function and avoid stiffness more than standard treatment that involves immobilization in a plaster for 3 weeks post-operatively.

Overall purpose:

Investigate if early mobilisation, starting exercise treatment 3 days after surgery, can lead to better elbow function and fewer complications than standard treatment in patient with fracture dislocation in the elbow.

Issues:

Can early mobilisation (starting 2-3 days after surgery) after fracture dislocation in the elbow lead to improved elbow function compared to usual treatment?

Can early mobilisation after fracture dislocation in the elbow lead to fewer stiff elbows?

Can early mobilisation after fracture dislocation in the elbow lead to fewer reoperations (capsule releases)?

Can early mobilisation after fracture dislocation in the elbow lead to improved patient satisfaction?

Material and method:

Recruitment

Patients over 18 years with a trauma operated at the University Hospital in Linköping with a radiological verified elbow fracture-dislocation will be asked to participate in the study

Inclusion criteria:

Patients over 18 years of age with radiologically verified fracture dislocation in the elbow operated on with internal fixation and or caput radi prosthesis.

Exclusion criteria:

Fracture caused by intentional violence

Ongoing malignancy or previous radiotherapy to the affected arm

Neurological disease

Cervicalgia or herniated disc

Associated vessels or nerve damage

Patient who does not want to participate in the study

Dementia

Inclusion procedure

Patients with a trauma operated at the University Hospital in Linköping with a radiological verified elbow fracture dislocation will be asked to participate in the study. A physiotherapist provides oral and written information about the study (Appendix X). If the patient accept to participate and meet all inclusion criteria, they are immediately after surgery randomised to one of the following groups; A) Early mobilisation where unloaded range of motion exercises are initiated 3 days after surgery and the plaster can be removed 5 times a day for performing those or to; B) Standard treatment which means that the patients are immobilised in a plaster for 3 weeks (usual regime). The same physiotherapist who informs the patients about the study performs the randomisation. Patients are consecutively randomised using a computer-based system which assign the patients group affiliation. The number and group affiliation (A or B) becomes the patient code. Patients receive oral and written information about the study and are asked if they want to participate before the surgery if possible otherwise immediately after surgery. If the patient agrees to participate, a physiotherapist, who is not involved in the rehabilitation and follow-up of these patients, will hold the randomization and fill in all the data into the computer based system that will randomly assign the patients to either early mobilisation or standard treatment. Thereafter, the physiotherapist including the patients will contact the treating physiotherapist at the orthopedic clinic. The patient will the get information regarding restrictions and continued rehabilitation. The patients in the early mobilisation group will primarily manage their training at home with the support of a physiotherapist who sees the patient once a week for the first 3 weeks. Patients will document the movement training in an exercise diary. After 3 weeks, all patients will follow the usual rehabilitation guidelines and continue their training with the help of a physiotherapist in primary care. Home training will continue to be important and will be documented in an exercise diary. All

patients will be followed-up by physiotherapist and then a medical doctor according to current practice 3 weeks and 3 months after surgery. There will also be a follow-up after 12 months and this is outside the usual clinical practice.

At 3v, 3- and 12 months, the following variables will be evaluated; *Primary outcome measure:* Elbow function is evaluated with the Oxford elbow score (Dawson et al), which is a disease-specific questionnaire that assesses pain, function and psychological status related to the elbow joint. The questionnaire has 12 questions with five answer alternatives in three subscales (pain, function and psychosocial impact). Each subscale gives a maximum of 16 points and in total the three subscales result in a value somewhere between 0-48 where zero is poor function and 48 is good function. Each subscale can then be converted to a value between 0-100 points. The lowest clinically relevant value where patients themselves experience that there has been a change is 10 points in subscale elbow function (Guyver et al). Our primary time point will be the difference in elbow function between the two groups at 12 months. Secondary dimensions: Activity level - The activity scale is an instrument designed for the patient to rate their degree of activity before the injury and after 1 year to be able to assess whether the patients have returned to their previously estimated activity level. Mobility: Flexion and extension as well as pronation and supination will be measured with a digital goniometer starting in the anatomical basic position. Patient satisfaction - patient global impression of change (PGIC) (Ferguson et al). Subjective seven-point scale with questions about satisfaction after treatment. The number of reoperations and other complications will be documented in the two groups. Heterotopic ossification - X-ray examination at 3 weeks, 3 months and 12 months

Sample size calculation We based the calculation on the primary outcome measure Oxford Elbow Score where we need 27 patients in each group to detect a difference of 10 points between the groups in subscale function (0-100) with a standard variation of 13 points ($\beta = 0.80$, $\alpha = 0.05$). A difference of 10 points has been proven a clinically relevant difference (Guyver et al).

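### The patient code includes the treatment letter, so a record or image labelled with it could reveal the arm; a neutral study number would close that route

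*Protocol*

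**What the plan says.** All the relevant text is in the protocol, in the section Inclusion procedure and the outcome paragraph that follows it.

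- **The code.** "The number and group affiliation (A or B) becomes the patient code".
- **The key.** The two letters are defined in the same section: "A) Early mobilisation where unloaded range of motion exercises are initiated 3 days after surgery" and "B) Standard treatment which means that the patients are immobilised in a plaster for 3 weeks".
- **Separation of roles.** The only independence described concerns randomisation, by a physiotherapist "who is not involved in the rehabilitation and follow-up of these patients, will hold the randomization". After that, "the physiotherapist including the patients will contact the treating physiotherapist at the orthopedic clinic".
- **Follow-up.** At the two earlier visits, "patients will be followed-up by physiotherapist and then a medical doctor according to current practice 3 weeks and 3 months after surgery". For the last visit: "There will also be a follow-up after 12 months and this is outside the usual clinical practice".
- **The outcome used here as an example.** Among the secondary measures: "Heterotopic ossification - X-ray examination at 3 weeks, 3 months and 12 months". The protocol gives no reader, image label or grading.

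No second, group-neutral identifier appears in the document.

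**The concern.** A patient code is normally what appears on case record forms, data files and sometimes images. If it contains the allocation, it takes the allocation wherever it goes. Patients and treating staff in this trial cannot be masked, because they know whether the plaster comes off for exercises. Other people who handle trial material need not know the arm, and a code with the letter in it removes that possibility for no stated purpose.

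The reading of X-rays for heterotopic ossification is the clearest example. It calls for judgement and can be done without meeting the patient. A reader who knew the arm could also have an expected direction: the Background says that ossification can lead to stiffness and links it to the length of immobilisation, and the closing paragraph of the protocol puts forward less stiffness with early mobilisation as the hypothesis. At stake is the credibility of a secondary outcome, not the primary comparison.

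**Working it through.** The point tests no figure in the plan, so the check is mainly a reading of the text.

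**Step 1. Does the code disclose the arm?** The code is the number plus A or B, and the protocol prints what A and B mean. Anyone who knows that key can read the arm from the code. This follows from the definition alone.

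**Step 2. Does the protocol offset this?** Two things could do so: a neutral identifier used for some purposes, or a stated separation between the code and those who judge outcomes. Neither is described. The independence of the randomising physiotherapist ("who is not involved in the rehabilitation and follow-up of these patients, will hold the randomization") covers the act of randomising, not the handling of coded images or data.

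**Step 3. What must be true for the code to do harm?** Three conditions are needed together:

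1. The record or image carries the study code. The protocol does not say which records do; films could be filed under another identifier.
2. The person handling it knows what the letters mean. The key is in the protocol, but nothing says whether the reader has seen it.
3. That person would not otherwise know the allocation. At three weeks and three months the visits follow current practice, with staff who may already know it. The twelve-month visit lies outside usual practice, so there the study can most easily set its own labelling.

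The documents neither establish nor exclude any of the three for the X-ray reader. The conclusion is therefore conditional: the code *could* reveal the arm.

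**Step 4. Scope.** The input is 27 patients per group, from Sample size calculation. That figure reproduces by the normal approximation, taking the printed 0.80 as power and α as two-sided: 2 × (1.96 + 0.84)² × 13² / 10² = 26.5, rounded up to 27. It does not depend on how patients are coded. If exactly 27 per group are recruited and all attend:

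- patients: 2 × 27 = 54
- X-ray examinations: 54 × 3 = 162
- at the two visits under current practice: 54 × 2 = 108
- at the twelve-month visit: 54

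These are counts of planned examinations, not of examinations shown to be exposed, and they say nothing about bias.

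**Step 5. Does the primary outcome depend on the code?** No. The Oxford Elbow Score is completed by patients, who know their treatment whatever the code says.

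**The case against.** The strongest case on the other side is that no harm is documented. Nothing says that X-rays carry the study code, who reads them, or that this person knows the key. The protocol nowhere promises blinded assessment, so the code contradicts no stated safeguard. If the reader is a follow-up doctor who already knows the arm, or if the films carry another identifier, changing the code does nothing for ossification. That outcome is also the last secondary measure listed and is not named in the four questions under Issues.

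Most of this stands, and it sets the limits of the point. A reader of the protocol might infer more, in four ways that the document does not support:

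- *That X-ray readers are unmasked.* This needs facts about labelling and staffing that the protocol does not give.
- *That the lack of described masked reading is an error in itself.* It is missing text; it neither states anything wrongly nor contradicts other text.
- *That goniometry or the data analysis is compromised.* The first depends on an assessor who is not named. The second depends on a statistical analysis plan that is not at hand.
- *That the size of the effect can be read from the group size.* With present/absent scoring (an assumption), one film classified differently would move a group's proportion by 1/27 = 3.7 percentage points. That holds for any yes/no outcome with 27 per group and says nothing about how often the code would cause it.

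What the objection does not remove is the sentence itself. The coding rule is stated in the protocol, not left open, and it creates a disclosure route for which no purpose is given.

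**Conclusion.** The concern holds in a limited form. The protocol fixes a patient code that contains the arm, prints the key, and describes no neutral alternative. Any study record or image labelled with the code could reveal the arm to a person who knows the key and would otherwise not know the allocation. The reader of the X-rays for heterotopic ossification is one example.

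This is an avoidable route of disclosure, not demonstrated unmasking. Its effect cannot be sized from the document and may be nil. Sample size, eligibility and treatment are untouched, as is the patient-reported primary outcome. Confidence is high about what the code contains and that it is avoidable, and low about whether it would change any reading. Priority is low: a cheap improvement that the sponsor could make.

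**What to change.** In Inclusion procedure, replace the sentence that defines the code with: *The study number alone, without group affiliation, is the patient code.* Keep the allocation in the computer-based randomisation system and link it to the data after outcome data are recorded. Where X-rays are labelled for the study, use the study number only. No additional reader is required.

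One practical condition applies: the number must be unique across both groups. The protocol does not say whether numbering runs in one sequence or separately within each group; in the second case, dropping the letter would leave duplicates.

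**Cost.** One replaced sentence, a short addition on labelling and linkage, and a linking list from the existing system. Treating staff must be told the group or look it up. The protocol already provides for contact with the treating physiotherapist, though it does not say what is passed on. Any codes already issued with the letter would need to be relabelled. The change does not mask staff who already know the allocation, so its benefit is confined to people who would otherwise learn the arm only from the code.

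### Could the pre-injury activity rating be collected after allocation and bias the return-to-activity comparison?

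*Protocol*

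**What the plan says.** Three parts of the protocol's Material and method bear on the point.

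- **Outcome schedule.** The paragraph on outcomes begins "At 3v, 3- and 12 months, the following variables will be evaluated". It lists no baseline assessment.
- **Activity level**, under the secondary dimensions. The item is described in its own terms: "The activity scale is an instrument designed for the patient to rate their degree of activity before the injury and after 1 year". Its stated purpose is "to be able to assess whether the patients have returned to their previously estimated activity level".
- **Inclusion procedure.** Patients are "they are immediately after surgery randomised to one of the following groups". They are approached earlier than that where possible, being "asked if they want to participate before the surgery if possible otherwise immediately after surgery". A physiotherapist with no part in rehabilitation or follow-up is to "fill in all the data into the computer based system that will randomly assign the patients". The items entered are not listed. In the early-mobilisation arm, "unloaded range of motion exercises are initiated 3 days after surgery and the plaster can be removed 5 times a day for performing those". The comparison arm stays in plaster for 3 weeks.

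**The concern.** Return to activity is judged against the patient's own account of activity before the injury, so that account is half of the outcome. If the listed visits are taken as the only occasions for collecting data, the earliest possible date for it is 3 weeks, after allocation. By then the arms have had very different experiences, and patients know which regimen they had. A patient whose elbow is doing badly may remember earlier activity as higher or lower than it was.

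If that tendency differed between arms, the reference value would itself be affected by treatment. The comparison would be biased by an unknown amount in an unknown direction, and no analysis could recover a reference that was not collected in time. For that reason the point cannot simply be passed to a statistical analysis plan. Some recall error is unavoidable in trauma patients, who are first met after the injury. Recall that depends on the arm is avoidable.

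**Working it through.** **1. What depends on this point.** The only calculated figure in the protocol is the sample size, for the Oxford function subscale: difference 10, SD 13, alpha 0.05 (two-sided assumed), power 0.80. By the normal approximation, n per group = 2 × (1.960 + 0.842)² × 13² / 10² = 2 × 7.85 × 1.69 = 26.5, rounded up to 27. The stated 27 is reproduced and uses nothing from the activity scale. The four questions under Issues concern elbow function, stiff elbows, reoperations and patient satisfaction. Return to activity is not among them.

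**2. The timing statements side by side.**

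| Statement | What it fixes | What it leaves open |
|---|---|---|
| General schedule: 3 weeks, 3 and 12 months | Follow-up assessments | Any data taken at inclusion |
| Activity item: before injury, and after 1 year | The two periods rated | Date of the first rating |
| Activity item: level previously estimated | That the reference comes from an earlier estimate | Whether that was before allocation |
| Inclusion procedure: data entered in the system that then randomises | That data are taken before allocation | Which items |

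The general schedule cannot apply literally to the activity scale. It would call for activity ratings at 3 weeks and 3 months, which the item's own description does not ask for. The specific sentence is better read as displacing the general one. The remaining rows then fit together: a rating made on an earlier occasion, and an inclusion contact at which data are entered before allocation. They do not prove that the rating is taken there. They make it the natural reading, and no statement conflicts with it.

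**3. How different the arms are by 3 weeks.** With exercises from day 3 and up to 5 plaster removals a day, the early arm may have had (21 − 3) × 5 = 90 exercise occasions by day 21, against none in the other arm. This shows that treatment experience differs. It says nothing about memory of activity before the injury.

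**4. Illustration of size.** The protocol gives no range or SD for the activity scale, so the bias cannot be calculated. As an assumption, take return to activity as yes/no, 27 per group, no true difference, and a true return rate p of 0.4, 0.5 or 0.6. Let recall move m patients in one arm from not returned to returned, so that arm's rate is p + m/27. One patient is 1/27 = 3.7 percentage points. The false-positive rate is the sum, over all pairs of counts significant at two-sided 0.05, of the product of the two binomial probabilities.

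| m | Shift (points) | Chi-square (p = 0.4 / 0.5 / 0.6) | Fisher's exact (p = 0.4 / 0.5 / 0.6) |
|---|---|---|---|
| 0 | 0 | 0.047 / 0.042 / 0.047 | 0.025 / 0.022 / 0.025 |
| 1 | 3.7 | 0.053 / 0.050 / 0.057 | 0.029 / 0.027 / 0.031 |
| 2 | 7.4 | 0.076 / 0.074 / 0.087 | 0.044 / 0.043 / 0.051 |
| 3 | 11.1 | 0.115 / 0.117 / 0.140 | 0.071 / 0.073 / 0.087 |
| 5 | 18.5 | 0.251 / 0.269 / 0.327 | 0.173 / 0.192 / 0.224 |

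Shifts of one or two patients leave Fisher's test at about 5% or below and raise chi-square to at most 8.7%. The inflation becomes serious only when three or more patients in one arm move in the same direction with none moving back. Both m and p are assumed; nothing in the protocol supports a particular value.

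**The case for a change.** The strongest case for a change is that the gap is real and cheap to close. No sentence places the pre-injury rating before allocation, and the activity wording could be read as both ratings being given at 12 months. The entry of data at randomisation names no items. When a measurement is taken is a data-collection matter that a protocol should settle. A few minutes with a short questionnaire at the existing inclusion contact would remove any doubt. If the sponsor already collects the rating then, writing it down costs nothing.

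Much of this stands. The date is not written, and later analysis could not repair a reference collected too late. What does not stand is the step from an unwritten date to a fault in the plan. No stated rule calls for late collection, and the wording leans the other way. Harm needs three further assumptions: that the rating was taken late, that recall differed by arm, and that the net shift was large and in one direction. The protocol supports none of them.

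The gain would also be partial. Activity at 12 months is still rated by patients who know their treatment, so the comparison stays open to treatment-dependent reporting wherever the reference comes from.

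**Conclusion.** No change to the plan is needed. The protocol leaves out a detail, the date on which the pre-injury activity rating is collected, and a study team would sensibly fill it by taking the rating at inclusion with the other data entered before allocation. The document contains no false statement or contradiction on the point, and no rule that produces a wrong result if followed.

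The possible effect is confined to one secondary outcome outside the four study questions. The primary comparison and the 27 per group are unaffected. Its size cannot be derived from the document. Under the assumed yes/no version, it runs from negligible for one patient reclassified in one arm (5.0-5.7% by chi-square) to substantial for five (25-33%), and only if the rating is in fact taken late. The conclusion rests on reading the activity item's own timing as taking precedence over the general visit list, and on the inclusion data plausibly containing the rating. If the rating were known to have been taken at 3 weeks or later, the return-to-activity result should be read with that in mind.
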